4.5 Description and justification of route of administration and dosage

Ertugliflozin is absorbed from the digestive tract and can therefore be orally administered.

Version number: 6.0 23-APR-2020

4.6 Dosages, dosage modifications and method of administration

Ertugliflozin will be administered in a dose of 15 mg/day.

4.7 Preparation and labelling of Investigational Medicinal Product

Study medication (ertugliflozin and matching placebo) will be provided by Merck. The pharmacy department of the University Health Network will be responsible for labelling and distribution of study medication to the participating sites. Study medication will be stored by the pharmacy unit of each participating centre in accordance with relevant guidelines.

4.8 Drug accountability

All study medications will be stored at room temperature at the pharmacy department of each participating centre. Study medication will be collected from the pharmacy department by the principle investigator at each participating centre. Non-used medication will be returned to the pharmacy department where it will be destroyed.

4.9 Handling and Dispensing

The investigational product should be stored in a secure area according to local regulations. The investigator is responsible for ensuring that it is dispensed only to study subjects and only from official study sites by authorized personnel, as dictated by local regulations. The investigator is responsible for ensuring that the investigational product is stored under the appropriate environmental conditions (temperature, light, and humidity), as described in section 6.1. If concerns regarding the quality or appearance of the investigational product arise, the investigational product will not be dispensed and Merck will be contacted immediately.

4.10 Drug Ordering

Initial Orders Contact the protocol manager at the UHN for information. *Re-Supply* Contact the protocol manager at the UHN ([contact]) for information.

When assessing need for resupply, institutions should keep in mind that shipments may take 10-15 business days as of receipt of request. Be sure to check with your pharmacy regarding existing investigational stock to assure optimal use of drug on hand.

5. NON-INVESTIGATIONAL PRODUCT

5.1 Name and description of non-investigational product(s)

Inulin (Inutest) or iohexol (Omnipaque) and paraaminohippurate (PAH), lithium carbonate (300 mg one day prior to each physiological study day i.e. on three occasions).

5.2 Summary of findings from non-clinical studies

Inulin and PAH have very low acute intravenous toxicities in mice and rats. Animal studies have shown that these agents have a very low protein binding and are well tolerated by the kidneys. The cardiovascular and neurotoxicity are low. Lithium will be administered on three separate occasions to measure tubular sodium handling. Plasma volume will be measured using a non-radioactive technique (indocyanine green dilution) to assess changes in plasma volume in response to SGLT2 inhibition

5.3 Summary of findings from clinical studies

Close to 100 per cent of the intravenously injected Inulin and PAH are excreted unchanged through the kidneys within 24-hours in patients with normal renal function. The elimination half-life is approximately 2 hours in patients with normal renal function. The protein binding of these agents is so low (<2%) that it has no clinical relevance and can therefore be neglected. In the doses used in this set of studies, lithium does not reach steady state and has no known risk.

5.4 Summary of known and potential risks and benefits

Measurement of GFR and effective renal plasma flow by plasma clearance of Inulin and PAH has not been associated with reports of adverse events, but should be avoided in subjects with known intolerances to these agents. Lithium will not be used in patients with a known intolerance to this medication. Iohexol will not be administered in patients with known allergic reactions to this substance or to iodine based solutions. Iohexol has a very low risk of causing allergic reactions, and anyone with an allergy will be treated appropriately by the study team and will not receive it again on future study visits.

5.5 Description and justification of route of administration and dosage

Inulin (or iohexol) and PAH will be intravenously administered according to established UHN protocols through an injection catheter.

5.6 Drug accountability

Inulin (or iohexol) and PAH will be stored at room temperature at each site. Inulin (or iohexol) and PAH and lithium will be collected from the pharmacy department by the principle investigator at each participating center in the morning of the study visit.

6. METHODS

6.1 Study parameters/endpoints

6.1.1 Main study parameter/endpoint

• Fractional excretion of sodium, using lithium clearance as a surrogate for proximal tubular sodium handling.

6.1.2 Secondary study parameters/endpoints (if applicable)

- Glomerular Filtration Rate and Renal plasma flow measured with inulin and PAH, as well as derived renal hemodynamic parameters as described elsewhere.²⁵ In the event that inulin is not available to measure GFR, then iohexol will be used, provided that there is no history of allergy to iodine based substances.
- Systolic/diastolic blood pressure, heart rate
- Echocardiography for markers of systolic and diastolic function, cardiac output (29)
- Arterial stiffness
- Plasma volume will be measured using a non-radioactive technique (indocyanine green dilution) to assess changes in plasma volume in response to SGLT2i (20, 27).
- Extracellular water, will be measured non-invasively using bioimpedence spectroscopy, as described elsewhere(28).
- Cardiac output and systemic vascular resistance will also be measured using non-invasive cardiac monitoring (NICOM). This non-invasive technique is a form of bioelectrical impedance ("bioreatance") to measure thoracic fluid content with electrocardiogram electrode stickers. Beat-to-beat changes in fluid content can be used to derive cardiac output. Then, using measured mean arterial pressure, systemic vascular resistance can be calculated. This entire measurement process takes approximately 15 minutes.
- Neurohormones/biomarkers
 - Hormones of the RAAS (renin, aldosterone in plasma and urine)
 - Natriuretic Peptides
 - Sympathetic nervous system markers
 - Urinary adenosine

6.1.3 Other study parameters (if applicable)

- Number of hypoglycaemic episodes
- Serious Adverse Events
- Drug related adverse events (causality to investigational product assessed by research physician).

6.2 Randomisation, blinding and treatment allocation

Treatment ertugliflozin and placebo will be randomized. A computer generated randomized code generated by UHN will be used. The pharmacy of each participating centre will store the randomization code.

6.3 Study procedures

Physical examination

Patients will be subjected to physical examination by the principal investigator before inclusion. This physical examination entails a routine investigation of heart, lungs and abdomen. At each visit patients will be asked for adverse events related to urinary tract infections or genital infections.

• 24hr urine collection

Patients are asked to collect 24hr urine at start and end of each treatment period to monitor albuminuria. In total, three 24hr urines are collected during the course of this study. 24hr urine collection instructions will be provided to each patient. The volume of the urine containers is determined when the patient delivers the urine at each visit. Subsequently part of the urine is used for clinical chemistry measurement and the other part stored per instructions in the laboratory manual.

Renal hemodynamic function

GFR and plasma flow measurements will be performed during each of the three physiological assessment visits.

The central laboratory at the UHN will be providing detailed instructions for the renal function tests in a separate laboratory manual. The inulin/PAH will be bought by the investigational site and should be used in accordance with the approved product label and manual instructions. In the event that inulin is not available, then iohexol will be used instead according to label and laboratory manual instructions.

Subject preparation:

After a 10-hr fast, two intravenous (IV) catheters, one in each arm, will be placed in the subject's antecubital vein. One line will be used for the injection of renal function marker solutions. The second line will be used for intermittent blood sampling. On each long study day (Visits 3, 4 and 8), study medication will be taken between after arrival in the laboratory **BEFORE** physiological measurements are obtained.

Blood pressure measurements

Blood pressure will be measured by office blood pressure machine during the outpatient visits. Patients will be in a semi-supine position during the blood pressure measurement. The average of three readings will be used.

Venipuncture

At each of the visits, approximately 20 ml will be taken for routine blood tests (approximately 20 ml/ 7 visits = 140 ml). At each of the 3 visits to assess kidney function, approximately 24 ml will be taken (total 72 ml), plus another 20 ml at each kidney function visit for measurement of hormones and other factors associated with kidney disease (approximately 20 ml for each of the 3 kidney visits = 60 ml). At the end of each of the 2 treatment periods (Visits 4 and 8), 9 blood samples of 1ml will be taken for ertugliflozin PK analysis (total 18ml). A total of approximately 290 ml of blood will be collected over 12 week period. Additional blood sampling will be take for plasma volume and lithium/sodium excretion measurements as described in the ICF.

- Laboratory measurements All routine laboratory measurements of this study will be assessed at the local laboratories of participating centres.
- Ertugliflozin plasma/urine concentration measurement At the end of the treatment period, during the GFR assessment, a 6 ml blood sample will be drawn for ertugliflozin and its metabolite ertugliflozin-3O-glucuronide measurement.

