7.2.3 Adverse events of interest

Urinary tract infection or genital infections

All potential events of urinary tract infection or genital infections will be recorded in the eCRF.

Diabetic ketoacidosis (DKA)

All potential events of DKA will be recorded in the eCRF.

Volume depletion

Events of volume depletion (eg, dehydration, hypovolemia, or hypotension) will be collected on the eCRF as AEs.

Fractures

All fractures will be recorded in the eCRF as AEs and on a separate eCRF page.

Major hypoglycaemic event

A major hypoglycaemic event is defined as an event that requires assistance of another person to actively administer carbohydrates, glucagon, or take other corrective actions. Plasma glucose concentrations may not be available during an event, but neurological recovery following the corrective actions is considered sufficient evidence that the event was induced by a low plasma glucose concentration. Major hypoglycaemic episodes will be recorded in the eCRF as an AE and on an additional eCRF page.

Acute Kidney Injury

Acute kidney injury is defined as an increase of 40% in serum creatinine from the previous visit or hospitalization due to acute kidney injury. All acute kidney injury events will be recorded on a separate eCRF.

Amputation and related events:

Amputations and related events will be recorded in the eCRF. Information on the actual amputations will be captured on a specific eCRF page.

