The Investigator will assess causal relationship between Investigational Product and each SAE/DAE, and answer 'yes' or 'no' to the question 'Do you consider that there is a reasonable possibility that the event may have been caused by the investigational product?'

Adverse Events Based on Signs and Symptoms

All AEs/SAEs/DAEs/AE of special interest spontaneously reported by the patient or reported in response to the open question from the study personnel: 'Have you had any health problems since the previous visit/you were last asked?', or revealed by observation will be collected and recorded in the eCRF. When collecting AEs/SAEs/DAEs/AE of special interest, the recording of diagnoses is preferred (when possible) to recording a list of signs and symptoms. However, if a diagnosis is known and there are other signs or symptoms that are not generally part of the diagnosis, the diagnosis and each sign or symptom will be recorded separately.

Adverse Events Based on Examinations and Tests

The results from protocol mandated laboratory tests and vital signs will be summarised in the clinical study report. Deterioration as compared to baseline in protocol-mandated laboratory values, or vital signs will be reported as AEs if they fulfil any of the AE criteria. If deterioration in a laboratory value/vital sign is associated with clinical signs and symptoms, the sign or symptom will be reported as an AE and the associated laboratory result/vital sign will be considered as additional information. Wherever possible the reporting Investigator uses the clinical, rather than the laboratory term (e.g., anaemia versus low haemoglobin value). In the absence of clinical signs or symptoms, clinically relevant deteriorations in non-mandated parameters should be reported as AE(s). Any new or aggravated clinically relevant abnormal medical finding at a physical examination as compared with the baseline assessment will be reported as an AE.

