- 2.7.The numbers of hypoglycemic events and serious adverse events will be reported for both the placebo group and ertugliflozin group. No statistical comparisons will be performed.

3. Analysis for exploratory objective:

- 3.1.– 3.3. The same models described in the analysis of primary objective 1.1 and 1.3 will be performed for each of the different outcomes.
- 3.4. The same models described in the analysis of secondary objective 2.1 will be completed, with changes in neurohormones as independent predictors, for changes in absolute measure of renal function as the dependent variables/outcomes.
- 3.5. The same models described in the analysis of secondary objective 2.1 will be completed, with changes in neuro-hemodynamic markers as independent predictors and changes in arterial stiffness as the different dependent variables/outcomes.

- 3.6. The same models described in the analysis of secondary objective 2.1 will be completed, with changes in neurohormones as independent predictors and changes to blood pressure as dependent variable/outcome.
- 3.7.– 3.8. The same models described in the analysis of primary objective 1.1 and 1.3 will be completed for each of the different outcomes.

Analysis population: The intention to treat population will be used for all analyses. There are no planned subgroup analyses for the primary outcome.

Hypothesis testing: For hypothesis testing, a 5% significance level will be used (two-sided). No interim analyses will be performed. For secondary objectives, nominal p-values will be reported.

General model assumptions and model diagnostic procedures: For the linear mixed-effects models with visit and treatment-by-visit interaction as covariates, a participant-level random intercept will be included. Restricted-maximum-likelihood will be used for estimation and the missing-at-random framework will be assumed. Plots of marginal and conditional residuals will be used for model diagnostics and assessment. Similar diagnostic procedures will be used for the linear regression models.

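### The safety objective counts all hypoglycaemic episodes, but only major ones are defined and have their own form, so non-major episodes rest on an open question and may be incompletely captured

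*Protocol*

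**What the plan says.** **What is to be counted.** The last secondary objective in Protocol section 1 characterises safety by hypoglycaemic episodes and serious adverse events. Protocol 6.1.3 lists "Number of hypoglycaemic episodes" without limiting it to severe cases. SAP Outcomes 2.7 names the same two outcomes, and SAP Analysis 2.7 states: "The numbers of hypoglycemic events and serious adverse events will be reported for both the placebo group and ertugliflozin group". It adds that the arms will not be compared statistically.

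**What is asked.** Protocol 6.3 contains one targeted safety question: "At each visit patients will be asked for adverse events related to urinary tract infections or genital infections". Section 11.1(j) repeats the focus on infections. For everything else, section 7.3 gives an open question, "Have you had any health problems since the previous visit/you were last asked", and records in the eCRF what patients volunteer, what they answer to that question, and what staff observe.

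**What is defined and recorded.** Section 7.2.3 defines a major episode as one in which another person has to step in, and provides: "Major hypoglycaemic episodes will be recorded in the eCRF as an AE and on an additional eCRF page". Non-major episodes have no definition and no page of their own.

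**The concern.** The SAP names two safety outcomes. Serious adverse events tend to come to notice by themselves. An episode that a patient corrects alone often does not, and it is the kind least likely to be called a health problem when the question is general.

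The protocol did not rely on the general question for infections, for which it added a specific prompt. It added none for hypoglycaemia, although a named objective depends on that count.

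At stake is how a low count would be read. The protocol expects hypoglycaemic risk to be low (sections 4.3 and 4.4), yet section 11.1(e) lists hypoglycaemia among the identified adverse reactions. If few episodes are recorded, a reader cannot tell whether few occurred or few were mentioned. Without a definition below major, a reader also cannot tell what was counted.

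**Working it through.** The plan gives no figure to reproduce. The check sets the passages side by side and then asks what can be said about size.

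**Step 1: scope of the count against the tools for collecting it**

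| | Major episode | Non-major episode | Urinary or genital infection |
|---|---|---|---|
| Within the SAP 2.7 outcomes | Yes | Yes | Only if serious |
| Definition (7.2.3) | Yes | None | None given |
| Listed as an AE of interest (7.2.2) | Yes | No | Yes |
| eCRF provision stated (7.2.3) | AE entry plus extra page | None specific | eCRF entry |
| Targeted question (6.3) | No | No | Yes |
| Open question (7.3) | Yes | Yes | Yes |

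The non-major column is the gap: inside the count, but reached only by the open question, spontaneous report or observation. Neither section 6.3 nor the schedule in section 2 mentions a diary, a review of meter readings or a hypoglycaemia prompt. Section 7.3 also lists the variables to be collected (dates, intensity, outcome and so on) for serious events, discontinuations and AEs of special interest. A non-serious, non-major episode that does not lead to discontinuation falls in none of these groups.

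**Step 2: share of episodes likely to be non-major**

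The documents give no rate. Section 3 excludes patients with severe hypoglycaemia in the two months before screening, with brittle diabetes, or with hypoglycaemia unawareness. It does not exclude insulin or other background glucose-lowering drugs. It is a reasonable assumption, but only that, that most episodes will be non-major.

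**Step 3: recall interval**

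Contacts after randomisation fall on days 7, 14–17, 42, 77, 84 and 91. The longest gap is 77 − 42 = 35 days, or five weeks, and the contact that closes it is by phone or email.

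**Step 4: effect on the counts**

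Let E and P be the true numbers of episodes on ertugliflozin and placebo, and s the share captured, equal in both arms.

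- Expected recorded counts: sE and sP.
- Difference: sE − sP = s(E − P), so it shrinks by the factor s.
- Ratio: sE / sP = E / P, so it is unchanged.

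The documents do not narrow s, which can lie anywhere from 0 to 1. Taking s = 0.6, 0.3 or 0.2 purely as assumptions, the recorded counts and their difference would be 60%, 30% or 20% of the true values, with the ratio unchanged. The true counts are also unknown, so no absolute number of missed episodes can be given.

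**The case against.** The strongest case for the plan has four parts.

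- **Patients are asked.** The open question is put by staff, covers the whole interval since they last asked, and all resulting events go into the eCRF. Open, non-leading questioning is a recognised method. This stands. A reader might infer that hypoglycaemia will certainly be under-counted, but without a capture rate the documents support only a risk of it.
- **The clinically important episodes are covered.** Major hypoglycaemia is an AE of interest with its own definition and page. This also stands, and it confines the point to non-major episodes. It does not close the gap, because neither the protocol objective nor the SAP limits the count to major ones.
- **The arms and centres are treated alike.** The trial is double-blind and section 7.3 prints the wording of the question. A reader might infer a biased comparison between arms, or counts that vary with each centre's probing. The documents show neither: equal capture leaves the ratio intact, and no centre difference is described.
- **The infection question has its own purpose.** It addresses a known risk of the drug (section 4.4), and visit questions need not mirror the SAP's tables. That is correct. The absence of non-serious infections from SAP 2.7 is a separate reporting matter. The infection prompt is relevant here only because it shows that the protocol uses specific prompts when it wants complete capture.

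The eCRF itself is not among the documents, so a prompt printed on it cannot be ruled out. If there is one, the protocol should say so.

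**Conclusion.** The point holds as a gap in definition and ascertainment. All hypoglycaemic episodes are to be counted, only major ones are defined and have a dedicated page, and non-major ones depend on an open question asked up to five weeks after the event. Incomplete capture is plausible, and its size cannot be derived from the documents.

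This rests on two assumptions: that patients do not always regard self-treated episodes as health problems, and that the eCRF holds no prompt the protocol leaves unmentioned. The statement that the ratio is preserved assumes equal capture in the two arms, which the blind makes reasonable.

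Severity is low. The count is descriptive and untested, in a 36-patient, 12-week mechanistic trial, and the primary analysis does not use it. The change is still worth making during conduct, because an episode nobody asked about is hard to recover at analysis.

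**What to change.** 1. **Protocol 6.3.** Extend the sentence on infections so that at every clinic, phone or email contact after randomisation staff also ask one fixed closed question about low-glucose episodes since the last contact, with the same wording at all centres.
2. **Protocol and SAP 2.7.** State what counts as an episode, major and non-major. The major definition already exists; the sponsor should supply the other.
3. **eCRF.** Extend the existing major-hypoglycaemia page to hold the number of episodes, their dates, the glucose value if measured, and whether help was needed.
4. **SAP 2.7.** Report, by arm, the number of episodes and the number of patients with at least one, separately for major episodes and for all episodes.

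**Cost.** One scripted question at each of the six scheduled contacts (Visits 4 to 9) and at any unscheduled one, plus a small form change. No extra visit, test or staff is needed. The downside is somewhat higher recorded counts in both arms, which will be less comparable with trials that rely on open questioning alone. If the change comes after enrolment has begun, the report should say from which date the closed question was used.
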